8.0 Data Review

8.1 Data Handling and Transfer

Data will be entered and exported as SAS® version 9.4 or higher datasets. Converted datasets will be created using SAS and following standard Clinical Data Interchange Standards Consortium Standard Data Tabulation Model conventions. Analysis datasets will be created using SAS and following CDISC Analysis Data Model standards.

Page 19 of 30

Medical history and AEs will be coded using the Medical Dictionary for Regulatory Activities (MedDRA), version 20.1 or later at the time of the analysis to assign a system organ class (SOC) and preferred term (PT) to each event. Prior and concomitant medications and steroids will be coded using the World Health Organization Drug Dictionary WHO DD 2017 SEP01 DDE+HD or later at the time of the analysis using anatomical therapeutic classification (ATC) and PT.

Additional details can be found in the PRA Data Management Plan, Data Transfer Plans, and the Data Quality Plan for this study. Data will be cleaned to prespecified levels for all data base locks or freezes, including for the interim and final analysis.

8.2 Data Screening

Beyond the data screening built into the PRA Data Management Plan, the PRA programming of analysis datasets and TFLs provides additional data screening. Presumed data issues will be output into SAS logs identified by the word "Problem" and extracted from the logs by a SAS macro and sent to Data Management.

Designated staff of BMS may be unblinded (obtaining the randomization codes) prior to database lock to facilitate the bioanalytical analysis of PK samples and immunogenicity.

9.0 Statistical Methods

All analyses will use SAS® version 9.4 or higher

- Descriptive summaries will be tabulated by part, treatment group, and in total within part unless otherwise specified.
- Categorical data will be presented using counts and percentages, with the number of participants in each category as the denominator for percentages
 - For by-visit summaries denominators will be adjusted to reflect the number of participants in the study at the time of the visit
 - Percentages will be rounded to one decimal place except 0% and 100% which will be displayed without any decimal places and percentages will not be displayed for zero counts.
- Continuous data will be summarized using the number of observations (n), mean, standard deviation (SD), median, first quartile, third quartile, minimum, and maximum unless otherwise specified. Minimum and maximum will be rounded to the precision of the original value.
 - Mean, median, first and third quartiles will be rounded to 1 decimal place greater than the precision of the original value. The SD will be rounded to 2 decimal places greater than the precision of the original value, with the original value having up to a maximum of 3 decimal places.
- P-values will be presented to 3 decimal places where presented in the TFL shells
- Separate tables, figures, and listings will be presented for Part 1 and Part 2 of the study. Data will not be pooled across Parts 1 and 2.

9.1 Participant Disposition

The number and percentage of participants in each analysis set will be presented. The number and percentage of participants randomized but not treated will be included.

The number of participants enrolled/randomized will be presented by study part, total within part and by treatment group, along with the number and percentage of participants who completed, discontinued, and are ongoing at the time of the data cut in total within part and by treatment group. The number and percentage of participants who completed the treatment period, withdrew from study treatment prematurely and a breakdown of the corresponding reasons for withdrawal from study treatment will be presented. The number and percentage of participants who completed the study, were ongoing at the time of the data snapshot (for the interim analysis report only), withdrew from the study prematurely, and a breakdown of the corresponding reasons for withdrawal will be presented. The summary will be presented by study part, treatment group, and total within part for the Randomized (RAS) Analysis Set. Also, by-participant listings will be generated.

9.2 Demographic and Baseline Characteristics

The following baseline demographic characteristics will be summarized by study part, treatment group and in total within part based on the RAS: sex, race, ethnicity, age, age group (<65 years, 65-<75 years, and >=75 years, as well as Adults [18-64 years], From 65-84 years, and 85 years and over), weight, height, body mass index (BMI).

The following baseline disease characteristics will be summarized by part, treatment group and in total within part based on the RAS: METAVIR liver fibrosis stage used for randomization as well as via central reader, history of impaired fasting glucose or diabetes, months from Hepatitis C sustained virologic response to randomization, and INR, baseline MRE, FibroScan, and CPA values, and baseline Pro-C3.

General medical history will be summarized for the Safety Analysis Set by part, treatment group, and in total within part. The number and percentage of participants with each event will be presented by SOC and PT. Note that counting will be by participant not event and participants are only counted once within each SOC and PT.

Prior medications summaries will be presented for the Safety Analysis Set by part, treatment group, and in total within part. The number and percentage of participants with each prior medication will be presented by ATC and PT. Note that counting will be by participant and participants are only counted once within each ATC and PT.

9.3 Important Protocol Deviations

Important protocol deviations will be summarized by number and percentage of participants experiencing each deviation category. All protocol deviations will be listed.

9.4 Prior and Concomitant Medications

Based on the Safety Analysis Set, prior and concomitant medications will be summarized by part, treatment group, and in total within part. The number and percentage of participants using each medication will be displayed together with the number and percentage of participants using at least one medication for each ATC and PT. A by-participant listing will also be presented.

9.5 Efficacy Analyses

All efficacy analyses, both primary and secondary, will be performed on the Modified-Intent-to-Treat (mITT) analysis set.

9.5.1 Primary Efficacy Analysis

The primary efficacy endpoint is the proportion of participants who achieve ≥ 1 stage improvement in fibrosis (METAVIR score) on biopsy after 12 weeks of treatment in Part 1. A "response" indicates the participant

Page 21 of 30

Statistical Analysis Plan Version Date: 19-Feb-2019

did achieve a ≥ 1 stage improvement in fibrosis. Summary tables will be provided for overall response and response by baseline METAVIR fibrosis stage via central reader (Stage less than 4, Stage 4), and shift tables will also be provided. Participants without an efficacy measurement at Week 12 will be considered as "non-responders". Spaghetti plots will also be provided for each treatment group.

9.5.1.1 Part 1

To evaluate the effect of BMS-986263 (90 mg QW) on METAVIR Fibrosis Stage at Week 12, a 95% exact CI of response rate for treatment versus placebo will be used to estimate the difference between the proportion of participants with \geq 1 stage improvement in fibrosis on liver biopsy. Additionally, the odds ratio of each treatment will be used to estimate improvement of treatment as compared to placebo for the proportion of participants with \geq 1 stage improvement in fibrosis on biopsy at Week 12.

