9.3.1.2 Analysis Methodology

Efficacy analyses will be performed using the modified intent-to-treat (mITT) population. The handling of missing values will be defined in the SAP.

Primary Endpoint Part 1: To evaluate the effect of BMS-986263 (90 mg QW) on METAVIR Fibrosis Stage at Week 12, a 95.0% CI of response rate for treatment vs placebo will be used to estimate the difference between the proportion of participants with ≥ 1 stage improvement in fibrosis on liver biopsy. Additionally, the odds ratio of each treatment will be used to estimate improvement of treatment as compared to placebo for the proportion of participants with ≥ 1 stage improvement in fibrosis on biopsy at Week 12.

Primary Endpoint Part 2: To evaluate the effect of BMS-986263 (45 mg Q2W, 90 mg Q2W, 90 mg Q4W) on METAVIR Fibrosis Stage vs placebo, a stratified Cochran Armitage Trend Test controlling for hepatic fibrosis stage (Stage 3 or Stage 4) will be used to analyze the proportion of participants with ≥ 1 stage improvement in fibrosis on biopsy at Week 24. After the assessment of trend, comparisons of each treatment group with placebo will be performed utilizing a stratified (fibrosis stage) Cochran Mantel-Haenszel test (CMH). All of these analyses will be performed at 1-sided 0.05 level of significance. In addition, 95% CI for the response rates and odds-ratios will be calculated.

A sensitivity analysis using an extended CMH correlation test will be used to assess the trend among the proportions for treatment groups with an adjustment to strata (fibrosis stage).³¹ Two-sided 0.10 level of significance will be used.

Secondary	Endpoints: No adjustme	ent will be made for multiplicity for
secondary	endpoints. Secondary	endpoints will be analyzed in
a similar method as the p	rimary endpoint unless otherwis	se specified in the SAP.

Continuous endpoints may be analyzed by analysis of covariance methods.

[figure not shown]
Categorical endpoints will be summarized using counts and percentages and when appropriate may be analyzed using categorical analysis methods.

[figure not shown]
Subgroup analyses will be performed including hepatic fibrosis stage.

[figure not shown]

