3.3 Randomization

[figure not shown]
Approximately 60 participants meeting eligibility criteria during the screening period for Part 1 will be randomized into the Part 1 treatment period. These participants will be randomized via IRT in a 1:2:1 ratio to 45 mg BMS-986263 QW, 90 mg BMS-986263 QW, or placebo QW in a double-blind manner. The randomization of participants will be stratified by fibrosis stage as assessed by local pathologist (METAVIR Stage 3 or Stage 4).

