4.9 Predetermined Covariates and Prognostic Factors

Subgroup analyses will be presented by baseline METAVIR fibrosis stage determined by central pathologist where specified in the TFL shells. Other subgroups may include Pro-C3 level (split at the median). Summary tables and/or figures may be provided for these analyses.

5.0 **Definitions**

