9.5.2.1 Collagen Proportionate Area

The change from baseline in collagen proportionate area will be analyzed using an Analysis of Covariance (ANCOVA) at Week 12 for Part 1. The model will include a fixed factor for treatment group and a covariate for baseline CPA. Contrasts will be used to compare the adjusted mean change from baseline between each treatment group and placebo and CIs will be presented for each comparison. In addition to actual, change from baseline, and percent change from baseline summaries by time point, box plots by treatment group and spaghetti plots by participant by treatment group will be provided.

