9.5.2.2 METAVIR and Ishak Fibrosis Scores

An analysis similar to that used for the primary efficacy variable will be conducted for secondary efficacy analyses of the proportion of patients with ≥1 or ≥2 stage improvement in liver fibrosis according to Ishak and METAVIR scores.

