9.5.2.3 MRE Liver Stiffness

[figure not shown]
An analysis similar to that used for the primary efficacy variable will be conducted for the proportion of participants with ≥15% decrease in MRE liver stiffness. An analysis similar to that used for the secondary endpoint of CPA will be conducted for continuous MRE liver stiffness.

Page 22 of 30

[figure not shown]

Protocol no: IM025006

Statistical Analysis Plan Version Date: 19-Feb-2019

Page 23 of 30

Protocol no: IM025006

Statistical Analysis Plan Version Date: 19-Feb-2019

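### Part 1 is randomised within locally read METAVIR stage, but no primary or secondary Part 1 estimate in the visible SAP conditions on it; a stratified supplement would be a cheap, optional improvement

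*SAP*

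**What the plan says.** **Design.** SAP 3.3: "The randomization of participants will be stratified by fibrosis stage as assessed by local pathologist (METAVIR Stage 3 or Stage 4").

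**Primary estimate.** SAP 9.5.1.1 plans an interval for the 90 mg versus placebo difference: "a 95% exact CI of response rate for treatment versus placebo will be used to estimate the difference between the proportion". It adds an odds ratio for each dose against placebo. Neither names stage.

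**Responder secondaries.** SAP 9.5.2.2 carries the method over: "An analysis similar to that used for the primary efficacy variable will be conducted for secondary efficacy analyses of the proportion of patients" improving on the Ishak and METAVIR scales. SAP 9.5.2.3 does the same for the MRE responder endpoint (at least a 15% fall in stiffness).

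**Continuous secondaries.** For CPA, SAP 9.5.2.1 states: "The model will include a fixed factor for treatment group and a covariate for baseline CPA". For stiffness, SAP 9.5.2.3 states: "An analysis similar to that used for the secondary endpoint of CPA will be conducted for continuous MRE liver stiffness".

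**Where stage does appear.** SAP 4.9: "Subgroup analyses will be presented by baseline METAVIR fibrosis stage determined by central pathologist where specified in the TFL shells". SAP 9.5.1 tabulates response by the central read (below Stage 4, Stage 4). The stratum itself appears once, in the baseline summary of SAP 9.2: "METAVIR liver fibrosis stage used for randomization as well as via central reader".

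**Purpose.** SAP 3.2 makes Part 1 an estimation exercise with no testing.

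**The concern.** A trial that stratifies its randomisation normally carries the stratification factor into the analysis. The allocation balances stage across arms. An interval that ignores stage does not take credit for that balance, so it is somewhat too wide when stage predicts response.

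Part 1's product is an estimate and its interval, from roughly 30 participants on 90 mg and 15 on placebo, so modest precision has some value. The plan also leaves open which stage reading a later adjustment would use. The local read defines the strata, while the central read is used for the displays. Fixing the choice in advance removes that freedom.

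What is at stake is a small amount of interval width and consistency between design and analysis. No test decision depends on it.

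**Working it through.** The plan gives no power, width or stage-specific response figure for Part 1, so there is no planned figure to reproduce.

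**Inputs from the documents**
- About 60 participants at 1:2:1 gives 15 / 30 / 15, so the primary comparison is 30 versus 15 (SAP 3.1). Missing Week 12 results count as non-response (SAP 9.7), so the denominators stay at all dosed participants.
- Response of 50% on active and 20% on placebo. These are Part 2 assumptions for 90 mg Q2W and placebo at 24 weeks (Protocol 9.1), borrowed for illustration.

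**Assumed inputs**
- Local strata of 15/15 on active and 8/7 on placebo.
- Stage gaps of 0, 20, 30 and 40 points in each arm. The stage-specific rates are 50/50 vs 20/20, 60/40 vs 30/10, 65/35 vs 35/5, and 70/30 vs 40/0.

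**Formulas**
- Unstratified Miettinen-Nurminen (MN): all δ with (d − δ)² ≤ 1.96² V(δ). Here V(δ) = [p1(1−p1)/n1 + p0(1−p0)/n0] × N/(N−1), and p1, p0 are the maximum-likelihood rates restricted to p1 − p0 = δ.
- Stratified MN: the same inequality with d = Σw_k d_k / Σw_k, w_k = n1k n0k/(n1k + n0k) and V = Σw_k² V_k(δ) / (Σw_k)².

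**One data set by hand: 15/30 vs 3/15**
- Crude difference: 0.500 − 0.200 = 0.300.
- Weights: 15×8/23 = 5.217 and 15×7/22 = 4.773, sum 9.990.
- Split 10/15 + 5/15 vs 3/8 + 0/7: stratum differences 0.2917 and 0.3333. Stratified estimate (5.217×0.2917 + 4.773×0.3333)/9.990 = 0.312.
- Split 8/15 + 7/15 vs 2/8 + 1/7: stratum differences 0.2833 and 0.3238. Stratified estimate 0.303.

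| Interval | 95% limits |
|---|---|
| Exact, score-ordered | −0.038 to 0.550 |
| Exact, ordered by raw difference | −0.026 to 0.586 |
| Unstratified MN | −0.007 to 0.532 |
| Stratified MN, first split | 0.021 to 0.540 |
| Stratified MN, second split | −0.008 to 0.536 |

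The SAP does not name its exact construction, so both are shown.

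**Mean 95% interval width over all possible outcomes**

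| Assumed stage gap (points) | 0 | 20 | 30 | 40 |
|---|---|---|---|---|
| Exact, score-ordered | 0.568 | 0.570 | 0.572 | 0.573 |
| Exact, raw difference | 0.607 | 0.608 | 0.609 | 0.610 |
| Unstratified MN | 0.526 | 0.530 | 0.532 | 0.534 |
| Stratified MN | 0.527 | 0.521 | 0.512 | 0.499 |
| Change due to stage | +0.1% | −1.6% | −3.7% | −6.6% |

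The stage effect is the comparison of the two MN rows (percentages from unrounded widths). The step from exact to unstratified MN is about 7% (1 − 0.526/0.568 = 7.4%) or 12–13% (1 − 0.526/0.607 = 13.3%). It comes from the interval method and has nothing to do with stage. Coverage is 96.6–98.4% for the score-ordered exact interval and 95.1–95.2% for stratified MN.

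**Less favourable cases**
- 80:20 stage mix: +0.1% to −1.4%.
- A 30-point gap on the central read with 80% local-central agreement leaves 18 points on the local read (30 × (0.8 − 0.2)): −1.3%.
- Active response of 20–35%: +0.4% to −4.7%.
- Rare responses: 10% vs 5% with no gap, 0.402 to 0.405 (+0.9%). At 5% vs 5% with all responders in one stage, 0.381 to 0.389 (+2.1%).

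**Covariance models.** As a rough guide, a factor with partial R² of r multiplies the width by √(1−r): √0.95 = 0.975 and √0.90 = 0.949. Simulation with arms of 15/15/30 and 14/13/27 gives −1.9% to −2.5% at an assumed 0.05, and −4.6% to −5.4% at 0.10. If stage adds nothing beyond baseline, the width rises by 0.1% to 0.7%.

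**The case against.** The strongest reply is that nothing here is broken. The analysis follows the protocol's Part 1 paragraph, the crude difference is unbiased under stratified randomisation, and the exact interval is valid. All of that stands. A reader might infer from the missing stage term that the Part 1 estimate is biased or its interval invalid; the documents do not support that.

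It is also true that the estimate itself hardly improves. At gaps of 0/20/30/40 points its sampling SD is 0.138/0.135/0.131/0.125 crude and 0.138/0.134/0.130/0.123 stratified. What shrinks is mainly the estimated variance.

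Stage is not ignored either. Response is shown by central-read stage, and the covariance models already adjust for a quantitative baseline measure of fibrosis. But a display by central stage is not a treatment estimate conditioned on the local stratum.

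A reader might also infer a contradiction with Part 2, where Protocol 9.3.1.2 plans "a stratified Cochran Armitage Trend Test controlling for hepatic fibrosis stage (Stage 3 or Stage 4) will be used to analyze" the primary endpoint. That is not supported. Stage control is stated there for Part 2's tests, with none stated for its intervals, odds ratios or covariance analyses, and Part 1 does no testing.

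Finally, a supplement has a price: it places a second interval on the primary endpoint. In the worked example the exact interval includes zero while one stratified interval does not. This objection stands and shapes the fix.

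**Conclusion.** The point holds as an optional improvement. In the visible text of SAP 9.5.1.1 and 9.5.2.1 to 9.5.2.3, no primary or secondary Part 1 treatment estimate conditions on the stage used for randomisation.

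One might go further and say that no Part 1 estimate anywhere does so. That cannot be established: some SAP text is blanked out, the TFL shells are a separate document, and the glossary lists CMH although the visible text never uses it.

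The size is small and conditional: +0.1% to −6.6% in interval width for the primary difference. This rests on assumed local-read stage gaps of 0–40 points, an even stage mix, and response rates borrowed from Part 2. The top of that range needs a 40-point gap on the local read. It would be wrong to credit stage with the further 7–13% between the exact and score intervals. No precision gain is claimed for the odds ratio.

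**What to change.** - **Covariance models (SAP 9.5.2.1, 9.5.2.3):** add the stage used for randomisation (local read) as a fixed factor for CPA and continuous MRE.
- **Responder endpoints:** keep the exact interval as primary. Add a labelled supplementary risk difference stratified by randomisation stage, with a stratified MN 95% interval, for METAVIR improvement of at least 1 stage, Ishak improvement of at least 1 stage, and the MRE 15% endpoint. Leave out the 2-stage endpoints, where responses may be too sparse for it to help.
- **Presentation:** print the unstratified MN interval beside the stratified one, so that the stage effect is not confused with the change of method. State in advance that the exact interval governs interpretation if the intervals differ.
- **Fallback:** if a stratum is empty in either arm, report only the exact interval.
- **Odds ratio:** if a Mantel-Haenszel version is added, label it as conditional on stage, because it estimates a different quantity from the crude one.

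**Cost.** SAP wording and a few lines of code. No new data are needed, since SAP 9.2 already tabulates the variable. The downsides are up to about 2% extra width if responses are rare, up to about 0.7% in the covariance models if stage adds nothing, near-nominal rather than guaranteed coverage for the supplement, and a second interval that may disagree with the exact one about zero.

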9.5.2 Secondary Efficacy Analyses

Secondary efficacy endpoints are as follows:

- Change in CPA, as compared to placebo after 12 weeks of treatment in Part 1
- Proportion of participants with ≥ 1 stage improvement in liver fibrosis (Ishak score), as compared to placebo after 12 weeks of treatment in Part 1
- Proportion of participants with ≥ 2 stage improvement in liver fibrosis (METAVIR score), as compared to placebo after 12 weeks of treatment in Part 1
- Proportion of participants with ≥ 2 stage improvement in liver fibrosis (Ishak score), as compared to placebo after 12 weeks of treatment in Part 1
- Proportion of participants with ≥ 15% decrease from baseline in liver stiffness as measured by MRE at Day 85 in Part 1
- Change from baseline in liver stiffness as measured by MRE Day 85 in Part 1

9.5.2.1 Collagen Proportionate Area

The change from baseline in collagen proportionate area will be analyzed using an Analysis of Covariance (ANCOVA) at Week 12 for Part 1. The model will include a fixed factor for treatment group and a covariate for baseline CPA. Contrasts will be used to compare the adjusted mean change from baseline between each treatment group and placebo and CIs will be presented for each comparison. In addition to actual, change from baseline, and percent change from baseline summaries by time point, box plots by treatment group and spaghetti plots by participant by treatment group will be provided.

9.5.2.2 METAVIR and Ishak Fibrosis Scores

An analysis similar to that used for the primary efficacy variable will be conducted for secondary efficacy analyses of the proportion of patients with ≥1 or ≥2 stage improvement in liver fibrosis according to Ishak and METAVIR scores.

9.5.2.3 MRE Liver Stiffness

[figure not shown]
An analysis similar to that used for the primary efficacy variable will be conducted for the proportion of participants with ≥15% decrease in MRE liver stiffness. An analysis similar to that used for the secondary endpoint of CPA will be conducted for continuous MRE liver stiffness.

Page 22 of 30

[figure not shown]

Protocol no: IM025006

Statistical Analysis Plan Version Date: 19-Feb-2019

Page 23 of 30

Protocol no: IM025006

Statistical Analysis Plan Version Date: 19-Feb-2019

